2.2 Phase 2 Objective

The objective for phase 2 of the study is to determine whether the extent of neuroinflammation has an impact on the severity and prognosis of clinical impairment.

To assess whether imaging of microglial activation predicts outcome and clinical progression in patients with stroke, the clinical status will be compared to the degree of neuroinflammation. The clinical status will be determined using:

A) The Modified Rankin Scale (mRS), which is being used in most stroke trials as a clinical indicator of the severity of impairment will be assessed.

B) The National Institutes of Health Stroke Scale (NIHSS), which provides a finer grained indicator of functional and neurological impairment will be assessed.

The neuro-inflammation will be assessed using:

A) A comparison between [¹⁸F]GE-180 PET findings with the extent of changes in proton diffusion and late structural damage by MRI will be determined.

2.3 Endpoints

Phase 1:

- 1) Data acquisition in 10 patients.
- 2) Technical feasibility analysis completed within 12 months. Assessing if it is possible to obtain quantifiable scans from patients with heterozygote genotype and that the frequency of the low-binding genotype (Thr147/Thr147) in this population is rare.
- 3) Tolerability levels recorded for 10 patients. The threshold for tolerability is the average score of neutral (score 3 out of 5) or better, as assessed by the tolerability questionnaire.

Phase 2:

- 1) Data acquisition on 50 patients (replacing the patients that are shown to have a low binders, genotype Thr147/Thr147, as assessed by the blood test)
- 2) Completion and analysis of the clinical assessments (performed 3 months apart) on 50 patients (replacing the patients with a low binders, genotype Thr147/Thr147, as assessed by the blood test).

It is expected that a few patients, even though they might not indicate that at the time of inclusion/consent, will leave the study before undertaking the PET scan. MRI scanning is usually perceived as the most stressful investigation because it involves the patient being scanned in a confined space and it also involves a significant level of noise, compared to PET scanning. Patients leaving the study at this stage before receiving the first PET scan, will be replaced by additional recruits. Patients, who leave the study at a later stage would not be replaced and counted as follow-up failures.

3.0 TRIAL DESIGN

3.1 Overall design

This study aims to recruit 50 patients in total receiving standard of care stroke assessments. Patients in phase 1 (n=10) will be asked to have two PET scans (using $[^{11}C]$ -(R)-PK11195 and

[figure not shown]
[¹⁸F]GE-180) and two MRI scans (one with and one without contrast). If the phase 1 analysis is favourable, the project will progress to phase 2. Patients in the second phase will be asked to have one PET scan (using [¹⁸F]GE-180) and two MRI scans (one with and one without contrast). All patients will remain on the study for 3 months after the onset of the stroke , at which point they will have outcome assessments (mRS and NIHSS). Following this, their participation in the study will cease and no further follow-up data will be captured. Patients will receive supportive care as per standard practice.

The study aims to recruit 10 patients in the first year, estimating a rate of 1 per month per NHS site, enabling 2 months for phase 1 review. Phase 2 estimated accrual for this study estimated at 2 patients per month. Thus, patient accrual is expected to be completed within 24 months. The total duration for phase 1 recruitment and analysis (12 months) analysis and phase 2 (24 months recruitment + 3 months for follow-up) recruitment is 39 months. The following 9 months will be dedicated to analysing the scans and completing coefficient correlation analysis on the outcome measure and the neuroinflammation. The total duration of the study is 48 months.

The study is designed to determine whether ¹⁸F-GE-180 PET as a biomarker can predict the clinical outcome in patients with cerebrovascular disease (CVD). Patients with sub-acute stroke of mild to moderate severity will be studied using standard research techniques and following the Quality Assessment of Diagnostic Accuracy Studies (QUADAS) criteria for diagnostic studies. In particular, the study protocol will ensure:

- patient selection based on standard diagnostic criteria
- short time interval between initial clinical assessment and PET
- verification of diagnosis at the time of follow-up
- independence of clinical diagnosis and clinical assessment from the result of the index test (PET) by blinding of clinical staff to PET results
- inclusion of failed and uninterpretable test results or withdrawal of consented patients into the final report

The selection of clinical instruments and the timing of assessments in the study are being guided by the design of major stroke trials and by diagnostic studies in vascular cognitive impairment.

Timeline after stroke

[figure not shown]

Figure 2. Schematic of the study procedure (Phase 1 and Phase 2)

3.3 Outcome measures

The primary outcome measure will be the functional score on the NIHSS at clinical follow-up after 3 months. The baseline value will be taken into account as a covariate. The Modified Rankin Scale and its change during follow-up will be analysed as a secondary outcome parameter.

 Imaging and outcome parameters will also be correlated with CRP as a marker of systemic inflammation. Regional image analysis will be performed to relate cognitive and motor symptoms with the brain location of structural abnormalities on MR and microglial activation on PET. Technical feasibility of the [¹⁸F]GE-180 scans and the possibility of reducing the scan time to 20 minutes are also among the outcome measures.

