	 Evaluating the tolerability of scanning using a questionnaire given to the participants, asking them to grade the discomfort associated with the [¹⁸F]GE-180 procedure on a 5 point scale, the average score must be neutral (score 3) or better. The technical feasibility will be assessed by evaluating the Translocator Protein TSPO on imaging using the [¹⁸F]GE-180 as the radiotracer. In particular, we will examine whether patients with the heterozygote genotype (identified by blood tests but analysed retrospectively), who are expected to present as medium binders, will provide quantifiable scans. A Correlation coefficient of 0.5 or higher between the focal abnormalities observed with the two different tracers in ischemic stroke patients, indicates that measurements are comparable.
	Phase 2 (months 13-39):
	 Examine whether the extent and intensity of microglial activation is related to functional outcome in stroke patients (disability scores, such as the NIHSS and the Modified Rankin Score, relative to initial assessment) Determine the location of microglial activation including infarct border zones and functionally connected brain regions in comparison with structural lesions as delineated on MRI and neurological deficits in patients after stroke Examine whether the intensity of microglial activation is related to systemic inflammation
Endpoints	1) Data acquisition in at least 10 patients and feasibility analysis completed within 12 months.
	2) Data acquisition on 50 patients (shown to not have homozygote genotype) and collection of functional outcome data (as assessed at 3 month follow-up).
	3) Analysis and statistical comparison of MRI/PET scans compared to the functional outcome.
Patient Group:	Ischaemic stroke patients (n=50 excluding patients with homozygote genotype)
Eligibility	Ischaemic stroke in MCA territory (I63.0 to I63.5), mild to moderate severity (Modified Rankin Scale score1-3)

(Recruited from the research hospital sites where initial clinical assessment is carried out and 3 month follow-up; All other procedures will be performed at WMIC and Central Manchester University Hospital NHS Foundation Trust).

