All second-generation tracers provide high-affinity binding with low background, but signal intensity is influenced by a genetic polymorphism (Ala147Thr) that has recently been identified on the TSPO gene [Owen *et al.* (2012)]. For each individual, the genetic polymorphism and the associated binding status can be determined using blood samples.

Previous PET studies of microglial activation in similar, but smaller patient groups using [¹¹C]-(R)-PK11195 have been conducted. In a study of volunteers at high risk for ischaemic stroke, a significant relationship of systemic inflammation, as indicated by increased plasma C-reactive protein (CRP) levels was found [Drake *et al* (2011)]. In another study in patients with mild cognitive impairment and Alzheimer's disease, increased microglial binding was found [Edison *et al.* (2008)]. A recently completed study in patients with gliomas compared to normal controls found an increased signal in malignant tumours and, to a lesser degree but still significant, also in normal brain tissue. Methods for TSPO receptor quantification using supervised reference tissue extraction techniques have been developed and validated [Turkheimer *et al.* (2007)]. Preclinical studies using [¹⁸F]GE-180 in WMIC laboratory demonstrated excellent TSPO binding [Owen *et al.* (2011)]. [¹⁸F]GE-180 uptake was significantly higher in the core of ischaemic lesions (+24%) and lower in the healthy contralateral tissue (-18%) than [¹¹C]-(R)-PK11195 and thus gave a significantly better contrast between the lesion and the healthy tissue. Full displacement of [¹⁸F]GE-180 was obtained within 5-10min post-injection of the cold ligand (Figure 1). Pilot studies in human patients are currently being conducted by GE Healthcare in Canada. These data also indicate that the biological properties of [¹⁸F]GE-180 are similar to 18F-DPA-714, suggesting high specific binding with moderate dependency on receptor activation status [Owen *et al.* (2011)].

[figure not shown]

Figure 1. Accumulation of [¹⁸F]GE-180 and displacement by cold [¹¹C]-(R)-PK11195 in an experimental ischemic infract [Dickens *et al.* (2014)].

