- The concentration of peripheral inflammatory markers such as C-Reactive Protein (CRP) and Interleukin 6 (IL6) in plasma will be measured. This is to study the relationship between markers of peripheral inflammation and markers of inflammation in the central nervous system.
- Genomic DNA will be extracted from whole blood (3ml EDTA tube). The affinity of the binding to [¹⁸F]GE-180 will be classified as high affinity binder (HAB), medium affinity binder (MAB) or low affinity binder (LAB) by analysing the rs6971 genotype of the participant (Owen et al., 2012).
- 3. Measurements of [¹⁸F]GE-180 activity in the venous plasma samples taken before and after the PET emission scan will be performed. These are used to assess whether the transient equilibrium analysis (Carson et al., 1993) is a valid approach and to optimise the time window past injection when the [¹⁸F]GE-180 emission scan is acquired.

During the study period, the treating clinician may have organised additional tests such as heart tests or other blood tests. Patients should be strongly encouraged to keep these appointments. It is routine for a patient to be offered a follow up appointment in the stroke clinic at approximately 6-8 weeks after their stroke. If the patient is an inpatient then we will liaise with the medical and therapy services in order to minimise any impact of travel to WMIC on the clinical care.

Three months (\pm 2 weeks) after the initial stroke patients will return to the hospital site for follow up. Patients will be assessed by the clinical team to assess if they have had any other symptoms that would indicate a recurrent stroke. The NIHSS and mRS will be assessed for second time as outcome measures.

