All analyses of clinical outcomes in the stroke survivors will be carried out using the *regress* command of *Stata*, incorporating inverse probability weights to allow for attrition using Stata's *pweight* option. The statistical significance of any predictive effects will be evaluated using robust standard errors, p-values and associated confidence intervals (using the Huber-White 'sandwich' estimator). Prediction models include the relevant PET scan variable, TSPO Ala147Thr polymorphisms (high versus medium) and the possibility of an interaction between the two. Other baseline demographic and clinical covariates will be added to the model so that the 'unique' contribution of the PET scan data can be assessed (i.e. how much information does it provide over and above the routinely collected demographic and clinical variables?). We will be giving considerable attention to confidence interval estimation rather just relying on statistical significance.

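### Section 3.3 does not carry the high/medium TSPO genotype term of section 11.4 into the PET-CRP correlation

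*Protocol*

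**What the plan says.** The Trial Summary lists among the phase 2 objectives: "Examine whether the intensity of microglial activation is related to systemic inflammation". Section 9.0 gives the purpose of measuring CRP and IL6: "This is to study the relationship between markers of peripheral inflammation and markers of inflammation in the central nervous system". The only analysis named is in section 3.3: "Imaging and outcome parameters will also be correlated with CRP as a marker of systemic inflammation".

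On genotype, section 1.1 says of second-generation tracers that "signal intensity is influenced by a genetic polymorphism (Ala147Thr) that has recently been identified on the TSPO gene". Section 2.3 replaces low binders, so the analysed group consists of high and medium binders. Section 9.0 provides for classifying participants by rs6971 genotype.

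Section 11.4 uses that information: "Prediction models include the relevant PET scan variable, TSPO Ala147Thr polymorphisms (high versus medium) and the possibility of an interaction between the two". The same paragraph sets its own scope at the start, "All analyses of clinical outcomes in the stroke survivors will be carried out using the" regress command of Stata. Its genotype term is therefore written for clinical outcomes.

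**The concern.** The GE-180 variable is treated as genotype-dependent when it predicts clinical outcome, but no such provision is written when it is related to CRP. Followed literally, section 3.3 puts high and medium binders into one correlation, and part of the spread in PET signal is then binding affinity rather than microglial activation.

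Two things follow. If genotype is unrelated to CRP, the extra spread lowers the expected correlation and its confidence limit. If CRP happens to differ between the two genotype groups, which can easily occur by chance in about 50 patients, the correlation can shift up or down for reasons unrelated to inflammation. Leaving the term open also leaves an analytic choice that could be made after the data are seen.

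**Working it through.** **The plan's own figure.** Section 11.1 states that 37 patients give a one-sided 90% interval with limit 0.200 for a correlation of 0.400. By Fisher's z:

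- n = (1.2816 / (atanh 0.40 − atanh 0.20))² + 3 = 36.65, rounded up to 37. The limit at n = 37 is 0.201.

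The figure reproduces. It concerns PET against clinical outcome; the protocol gives none for PET against CRP.

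**Inputs for the illustration.**

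- Within-genotype PET-CRP correlation of 0.40: assumed, borrowed from the minimum useful PET-outcome correlation in section 11.1.
- Share of medium binders p = 0.4: assumed; 0.3 and 0.5 were also tried.
- n = 50: the recruitment target in section 3.1. CRP is taken at the scan visit, so three-month follow-up does not reduce it.
- Gap d between high and medium binders, in within-genotype SDs of PET signal: not in the documents, so varied.

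**Attenuation when genotype is unrelated to CRP.** Genotype adds variance p(1−p)d² to a within-genotype variance of 1:

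- pooled r = 0.40 / √(1 + p(1−p)d²), with p(1−p) = 0.4 × 0.6 = 0.24
- d = 0.5: 0.40 / √1.06 = 0.389
- d = 1: 0.40 / √1.24 = 0.359
- d = 2: 0.40 / √1.96 = 0.286

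**Interval and power at n = 50.** The lower one-sided 90% limit is tanh(atanh r − 1.2816/√47). Power is for a two-sided 5% test, Φ(√47 · atanh r − 1.96). For the adjusted analysis √46 replaces √47, because one degree of freedom is used: tanh(0.4236 − 1.2816/6.782) = tanh(0.2347) = 0.230.

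| Analysis | r | Lower limit | Power |
|---|---|---|---|
| Pooled, no gap | 0.400 | 0.232 | 0.83 |
| Pooled, d = 0.5 | 0.389 | 0.219 | 0.80 |
| Pooled, d = 1 | 0.359 | 0.187 | 0.73 |
| Pooled, d = 1.5 | 0.322 | 0.146 | 0.63 |
| Pooled, d = 2 | 0.286 | 0.107 | 0.52 |
| Genotype-adjusted, any d | 0.400 | 0.230 | 0.82 |

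The medium-binder share matters little: at d = 1, pooled r is 0.364 for p = 0.3 and 0.358 for p = 0.5.

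**When CRP differs between genotypes.** With 20 medium and 30 high binders, the chance difference in mean CRP has a standard error of √(1/20 + 1/30) = 0.29 SD, so a difference of 0.3 SD is unremarkable. Let g be that difference:

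- pooled r = (0.40 + 0.24dg) / √((1 + 0.24d²)(1 + 0.24g²))
- d = 1, g = +0.3: 0.472 / √(1.24 × 1.0216) = 0.419
- d = 1, g = −0.3: 0.328 / √(1.24 × 1.0216) = 0.291

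A simulation of 400,000 draws gave 0.418 and 0.289. The pooled value can therefore lie above or below 0.40.

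**The case against.** The strongest reply is that the protocol never says the CRP correlation is unadjusted. Section 3.3 is a short list of outcome measures, and it names neither a coefficient nor a model for CRP. The document also uses the word correlation loosely: sections 3.1 and 10.0 describe the main PET-outcome analysis that way, and section 11.4 then specifies it as a regression with genotype. Covariates for a secondary association are often settled in the statistical analysis plan, which is not shown. A reader might infer that the protocol chose to ignore genotype here; the text does not support that. What stands is narrower. The protocol itself writes the genotype rule, limits it to clinical outcomes, and in section 3.3 names a covariate for NIHSS but none for CRP.

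Second, the effect may be small. Low binders are replaced, and section 11.3 uses within-patient target-to-reference ratios, which may remove some of the genotype difference. This is fair, and at a gap of 0.5 SD the loss is only 0.011 in r. But the protocol does not say that the ratio removes the effect, and section 11.4 keeps genotype in the models although ratios are planned.

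Third, a reader might infer that the PET-CRP correlation must be biased towards zero. That requires genotype to be unrelated to CRP. In a given sample the shift can go either way.

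Fourth, power is not the protocol's criterion: section 11.1 plays down formal power and favours interval estimation. The confidence limits in the working are therefore the more relevant measure.

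**Conclusion.** The point holds as a minor one. The genotype term is written for the clinical-outcome models and is not carried into the PET-CRP analysis, although the protocol recognises that genotype affects the signal.

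Under the stated assumptions, the cost of omitting it runs from negligible (r 0.39 at a 0.5 SD gap) through moderate (0.36 at 1 SD, lower limit 0.187 against 0.230 adjusted) to substantial (0.29 at 2 SD). The documents do not show where in that range the trial lies. The figures also assume that genotype shifts the mean signal without changing the slope on CRP, and the attenuation figures assume that genotype is independent of CRP.

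The second half of the sentence in section 3.3, clinical outcome against CRP, is not affected, because tracer binding plays no part in it. Nor are the primary NIHSS analysis and the n = 37 precision statement.

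**What to change.** Add one sentence to section 3.3: the relation between GE-180 imaging parameters and CRP will be estimated with TSPO genotype (high versus medium) as a covariate, for example as a partial correlation reported with its confidence interval. Leave the analysis of clinical outcome parameters against CRP as it stands. If the statistical analysis plan already says this, only the wording of 3.3 needs aligning.

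The genotype is already to be measured, so no data collection is added. The statistical cost is one degree of freedom: with no gap at all, the lower limit at n = 50 goes from 0.232 to 0.230.

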4.0 SELECTION OF TRIAL PARTICIPANTS

4.1 Inclusion criteria

Stroke patients (n=50):

- 1. Age: 18+
- 2. Ischemic stroke in MCA territory
- 3. Mild to moderate severity (Modified Rankin Scale score 1-3)

Patients must be able to give Informed consent or patients that wish to consent but are unable to sign or mark the consent form due to mobility issues may give their consent orally in the presence of at least one witness. The witness/es must sign the consent form as evidence that the information was accurately explained to and understood by the participant and that consent was freely given.

4.2 Exclusion criteria

- 1. Neurological diagnosis of neurodegenerative disease
- 2. Inability to understand study information and/ or express willingness to consent to the study due to communication difficulties (.
- 3. History of brain surgery, brain tumour, neuroinflammatory or neurodegenerative disease
- 4. Severe uncontrolled systemic illness
- 5. Patients in whom carotid endarterectomy/carotid stenting is due to be carried out within three months of recruitment to the study.
- Treatment with other drugs known to influence microglial activation, e.g. minocycline, Corticosteroids or Benzodiazepines (2 weeks prior to date of the scan).
- 7. Pregnancy / Breastfeeding women
- 8. Contraindications to MRI scanning
- 9. Patients receiving treatment with Antabuse (see appendix 1 for details)

4.3 Discontinuation / withdrawal of participants and 'stopping rules'

The study would be stopped if any previously unknown serious safety concerns were identified or if new information comes to light that makes the aims or objectives of the study futile or if requested by the study sponsor or funder.

4.3.1 Withdrawal of patients

When consenting to the trial, patients are consenting to trial procedure, trial follow-up and data collection. Patients will be withdrawn from scanning prior to completion for the following reasons:

- Adverse event or an intercurrent illness
- Unable to complete the visits or study documentation (such as questionnaires etc) as required
- Deterioration in health
- Patient decision
- Investigator decision
- For safety reasons e.g. recommendation of IDMC that trial should not continue.
- Benzodiazepines and other drugs known to influence microglial activation, e.g. minocycline or corticosteroids in the last three days prior to the PET scan
- If a patient is withdrawn from the PET scanning prior to having a tracer there is no need to complete the follow-up.

Patients will only be withdrawn from further follow-up in the case of:

• Patient explicitly stating their wish not to contribute further data to the study

4.3.2 Early discontinuation of trial

The early stopping rules for efficacy will be based on the phase 1 analysis. Depending on the outcome of this stage, we will either continue without modification, make appropriate modifications or, in case of insurmountable problems or poor tolerability of the scanning protocol will stop the study. This critical 'Go/No-Go' decision will also be based on advice from the trial steering committee, the sponsor and the funder, who will be informed about study progress, the results of the tracer comparison and patient feedback prior to the second milestone meeting. Efficacy will be based on:

- The comparison of the new tracer ([¹⁸F]GE-180) with the already established [¹¹C]-(R)-PK11195 in 10 patients.
- Patient tolerability questionnaire about the feasibility in terms of experience and comfort.
- Technical feasibility of the scans, whether the participants with the heterozygote genotype will provide quantifiable scans.

An Independent Data Monitoring Committee (IDMC) will be appointed who will oversee patient safety and any recommendations from the IDMC (which may include stopping the trial after phase 1) will be considered by the Trial Steering Group. The IDMC will be presented with the

phase 1 data for consideration and a decision whether to continue onto phase 2 will be reached before the end of month 12.

